#### **Efficacy Summaries**

In addition to the efficacy analyses described above, univariate descriptive statistics (number of observations, mean, standard deviation, univariate 95% confidence intervals, median, minimum, and maximum) will be provided for continuous variables, and counts and percentages will be presented for categorical variables.

#### **Safety Summaries**

The FAS population will be used for the analysis of safety data (AEs, exposure to study medication, clinical laboratory values, vital signs, and ECG).

AEs will be coded with the Medical Dictionary for Regulatory Activities. Treatment-emergent adverse events (TEAEs) are defined as AEs with an onset date on or after the date of first administration of study medication and before the date of last administration of study medication + 30 days. TEAEs will be presented by system organ class and preferred term in frequency tables. Patients with multiple AEs will be counted only once within each preferred term and system organ class. Key patient information for patients with an AE with an outcome of death, patients with SAEs, and patients with an AE leading to discontinuation of study medication will be listed.

Laboratory data (hematology, serum chemistry, coagulation, and urinalysis) will be converted to Système International units for reporting and processing purposes. Absolute values and changes from baseline will be presented descriptively. Laboratory data outside study specific reference ranges will be listed. Vital signs and ECG parameters will be presented descriptively.

#### 15.4 Interim Analysis

No interim analysis is planned for this study.

#### 15.5 Intercurrent Events and Missing Data

An intercurrent event is one that occurs after the first dose of study medication and either precludes the observation of the variable or affects its interpretation. The following is a list of negative intercurrent events related to the primary endpoint:

- Death
- Withdrawal from study
- Intubation and ventilation
- Rescue with a non-protocol specified treatment for cytokine release syndrome

The following is a list of positive intercurrent events related to the primary endpoint:

- Early discharge due to recovery

The patient will be considered a responder if the primary endpoint is missing following a positive intercurrent event. Patients will be considered a non-responder for all observations (missing or not missing) following a negative intercurrent event.

Missing data and intercurrent event imputation will be treated in a similar manner as the primary endpoint for secondary endpoints of a categorical nature. For secondary endpoints of a continuous nature, the last observation prior to the intercurrent event will be carried forward (LOCF) for all positive intercurrent events and the worst observation prior to the intercurrent event will be carried forward (WOCF) for all negative intercurrent events.

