##### 3.2.2 Secondary Endpoints

What is being measured	Measurement time frame	Measurement Tool
Change in 7 point-ordinal scale	Baseline, Day 3, Day 7, Day 14, Day 28 and follow-up.	Using WHO COVID-19 Ordinal scale measuring: Proportion and time to patients with greater than 2 point improvement on the 7 point categorical scale

Change in oxygen saturation-normalization	Baseline and continuous throughout hospitalization	Peripheral capillary pulse oximeter to measure: SpO 2 /FiO 2 ratio over time, sustainment of normalization in 24 hours, and relative shifts in SpO 2 /FiO 2 categories (<235, between 235 and 315, greater than 315) over time
Need for advanced respiratory care	Baseline and continuous throughout hospitalization	Derived from medical record: time of intubation in the ICU, duration of ICU care in days, duration of overall hospitalization in days
All-cause mortality	Baseline and through d60	Noted in patient medical record
Number and percent of adverse events (AEs) and serious adverse events (SAEs); mean change from baseline lab values, vital signs, and ECG	Baseline through day 14 or at discharge <d14, at d28 ±3, d45 ±3 and d60 ±3 (lab values will be examined up to d45) 	CTCAE v5.0; changes in CBC, CMP, Mg, PT/INR, PTT, GGT, hsCRP, D-dimer, LDH, ferritin, creatine kinase, troponin-i, procalcitonin; standard vital signs measurement with pulse ox; ECG
Proportion of participants with normalization of fever for 24h	Baseline through day 14 or at discharge <d14	Standard daily vital measurement and obtained from patient medical record
Development of new bacterial or fungal infection (AE of Special Interest)	Continuous throughout hospitalization	Noted in patient medical record
Incidence of ARDS  through day 14 or at discharge <d14	From day 1 though day 14 or at discharge <d14	Noted in patient medical record
Change in plasma cytokines IL-1β, IL-6, IL-8 and TNF-α	Baseline, day 3, day 7 (or discharge <d7), day 14 (or discharge >d7 and <d14)	Plasma collected from blood and assayed on Luminex panel performed by KUMC BBV Core

 For clarification, lab values will be collected at baseline, day 3, day 7 (or discharge <d7), day 14 (or discharge >d7 and <d14), at day 28 ±3, day 45 ±3. Vital signs, pulse ox will be collected baseline through day 14 or at discharge <d14, at d28 ±3, d45 ±3 and d60 ±3 (lab values will be examined up to d45)

 ARDS Criteria:

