#### 10.2 Duration of Follow Up

Survival follow up assessments will be conducted 28, 45 and 60 days post hospital day 1 and all participants should complete these visits. Exceptions include death, lost to follow-up or the participant withdrawing consent for follow-up all of which should be documented in the participants medical record and EDC.

Discontinuation from treatment does not preclude the need to complete follow-up assessments.

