 Most recent value recorded in EMR^2 Recorded daily vital signs through hospitalization course (baseline thru day of discharge or Day 28). Record vital signs from 00:00 – 24:00 each Day. Vital signs to include: highest and lowest heart rate, highest and lowest respiratory rate, highest and lowest temperature, Highest SpO2 and FiO2 concurrent to highest SpO2, Lowest SpO2 and FiO2 concurrent to lowest SpO2, weight (if available), BP with highest systolic value, and BP with lowest systolic value. For patients previously on hydroxychloroquine discontinued at randomization; 24 hours ± 2 hour after initiation of drug Research lab tubes to be collected per respective site instructions (see table page 32). record daily while in the hospital drug accountability SOC lab values will be collected daily throughout hospitalization course (baseline thru day of discharge or Day 28 if available) SOC arterial blood gas values will be collected if available Investigator to assess general appearance; head; neck; thyroid; eyes, ears, nose and throat (EENT); respiratory; cardiovascular; lymph nodes; abdomen; skin; musculoskeletal; neurological; other, specify. Investigator to assess changes from baseline in general appearance; head; neck; thyroid; eyes, ears, nose and throat (EENT); respiratory; cardiovascular; lymph nodes; abdomen; skin; musculoskeletal; neurological; other, specify. Prior and Concurrent meds will be recorded as far back as -30 days pre-enrollment Provide Appendix C patient self-directed instructions on how to perform buccal mucosa swabs Historic Lab Values can be used if test performed Day -2 through Day 0^13 Collect Highest O2 Supplementation of the day, options include, Room Air, Nasal Cannula or High Flow Nasal Cannula, Mask or Non-rebreather Mask, Heated High Flow (Comfort Flow), BiPAP or CPAP (excluding chronic CPAP use for sleep apnea), Invasive ventilation, ECMO, or Other (specify other). Also document Highest Oxygen Requirements (L/min), FiO2 concurrent to highest O2 requirement, Lowest Oxygen Requirements (L/min), FiO2 concurrent to lowest O2 requirements, and if patient is in ICU Prior to morning study drug dose It is possible that participant's date of discharge will change after Day of Discharge Assessments are performed. If this occurs, do NOT recollect research blood and urine, research buccal mucosa tissue brushing, research saliva, 24-hour COVID-19 PCR test, Phosphate, Cystatin C, and Urinalysis.

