### 11.4 Participant Discontinuation/Withdrawal from the Study

- Duration of therapy will depend on individual response, evidence of disease progression and tolerance. Any one of the listed items below will be defined as a stopping criteria event. Participants will be removed from protocol therapy for any of the unacceptable adverse event listed below. Participants will have study treatment withdrawn but will remain in the study for follow-up, if any of the following occur:
  - Intubation and ventilation
  - Intercurrent illness that prevents further administration of treatment.
  - Unacceptable adverse event(s) defined as:
    - Malignancy (except for non-melanoma skin cancers)
    - Hepatitis B re-activation
    - Rhabdomyolysis
    - Demyelinating disease
    - Heart failure
    - Lupus-like syndrome

- Hypersensitivity reaction
- Gastrointestinal perforation
- WBC  $<1 \times 10^3/\mu\text{l}$
- ANC  $<0.5 \times 10^3/\mu\text{l}$
- Platelet count  $<50 \times 10^3/\mu\text{l}$
- Hemoglobin:  $<6.5 \text{ g/dl}$
- AST, ALT:
  - $>5 \times \text{ULN}$
  - $>3 \times \text{ULN}$  and (total bilirubin  $>2 \times \text{ULN}$  or international normalized ratio [INR]  $>1.5$ )
  - $>3 \times \text{ULN}$  with appearance of fatigue, nausea, vomiting, right upper quadrant pain or tenderness, fever, rash and/or eosinophilia ( $>5\%$ )
- Serum creatinine:  $>2 \times \text{ULN}$
- Serious bacterial or fungal infection
- Other major developing illness or conditions at the discretion of the treating physician
- Participant demonstrates an inability or unwillingness to comply with the oral medication regimen and/or documentation requirements
- Participant decides to withdraw from the protocol therapy
- General or specific changes in the participant's condition render the participant unacceptable for further treatment in the judgment of the treating investigator
- Major violation of the study protocol (i.e., unable to adhere to study schedule) that in the opinion of the treating investigator, puts the participant at undue risk
- Discontinuation of the study by KUMC
- Confirmed pregnancy
- Completed Overall Survival (OS) follow up as per protocol
- Lost to follow-up
- Death

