Descriptive statistics (number of observations, mean (standard deviation) or median (minimum, maximum)) will be provided for continuous variables, and counts and percentages will be presented for categorical variables for each group.

Primary Efficacy Analysis

The study is hypothesis generating. The primary assessment of efficacy for this study will be the point estimate and corresponding exact 90% confidence interval for the proportions of responders for the ATI-450 and Placebo groups. All subjects who are alive, free of respiratory failure (do not require supplemental oxygen) by Day 14 of the trial will be considered responders. The point estimate and corresponding 90% confidence interval will be derived based on sample proportions and the Copper-Pearson CIs for proportions for the two groups (categorical data analysis by Alan Agresti, 3rd edition).

Secondary Efficacy Analyses

Binary variables will be analyzed using the method like that described for the primary endpoint. In addition to the point estimate and confidence interval for the difference in proportions for binary endpoints, odds ratios, corresponding confidence intervals will be provided. For binary measures that are recorded over time, separate analyses will be conducted at each timepoint.

Continuous secondary efficacy endpoints will be analyzed by estimating group means and mean difference and 95% CIs at each time point. Missing data will be imputed with the single imputation methods described above (LOCF or WOCF).

For time to discharge from hospital, estimates of the median (50th percentile) will be provided for each treatment group and Kaplan-Meier Curves will be provided. A two-sided stratified log-rank test will be applied. The stratification factor will be baseline age group (<60 versus ≥ 60).

Exploratory Outcomes Analyses

For all the Cytokines, changes over time (baseline, d7, EOT, d28) will be summarized by descriptive statistics and trajectory plots. Any time point after the end of treatment (EOT) will not be measured.

Safety Summaries

AEs will be summarized using table format based on DSMB requirements (attached).

Missing Data Imputation

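### The carry-forward rule for continuous endpoints draws only on values from before the intercurrent event, so a ventilated or deceased patient can be entered at too mild a score, and Protocol and SAP differ on whether measured values are replaced

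*Protocol*

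**What the plan says.** Protocol 15.5 lists death, study withdrawal, intubation and ventilation, and rescue treatment for cytokine release syndrome as negative intercurrent events, and early discharge due to recovery as the positive one. For continuous secondary endpoints it then sets two rules. Where the event is negative, "the worst observation prior to the intercurrent event will be carried forward (WOCF) for all negative intercurrent events". Where the patient goes home recovered, the most recent value taken before discharge is used instead. Neither rule carries a condition about missingness.

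For the primary endpoint the same section is explicit. After a positive event the patient counts as a responder only if the endpoint is missing. After a negative event, "Patients will be considered a non-responder for all observations (missing or not missing) following a negative intercurrent event".

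The SAP repeats the two carry-forward rules under Missing Data Imputation. Under Secondary Efficacy Analyses it says "Missing data will be imputed with the single imputation methods described above (LOCF or WOCF".

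The Protocol keeps collecting data after these events:

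- Section 11.4, which covers intubation: "Participants will have study treatment withdrawn but will remain in the study for follow-up".
- Section 10.2: "Discontinuation from treatment does not preclude the need to complete follow-up assessments".
- Section 9 keeps patients who are discharged early on study.
- Schedule of Events, footnote 2: "Recorded daily vital signs through hospitalization course (baseline thru day of discharge or Day 28". This record includes SpO2 and the concurrent FiO2. Footnote 13 adds the level of oxygen support, with invasive ventilation and ECMO among the options.
- The Day 28 visit repeats SpO2/FiO2, the WHO scale and laboratory tests.

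**The concern.** A worst-value rule is meant to stop a patient who deteriorates from being entered as though nothing had happened. Confined to values from before the event, it cannot do that when the event is itself the deterioration. Intubation and death mark states worse than anything recorded earlier on the WHO scale, so the carried value describes a milder patient.

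The documents also leave room for two different analysis datasets. A programmer working from Protocol 15.5 could replace every post-event value, measured or not. One working from the SAP would fill only the gaps. In a trial with about 10 patients per arm, a few patients handled differently can visibly move an arm mean.

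**Working it through.** The plan gives no figure for this rule, so there is nothing to reproduce. The check sets the rule against the scale and the visit schedule.

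**Inputs**

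- WHO scale (Protocol Appendix B): ambulatory 1 or 2; hospitalised without oxygen 3; oxygen by mask or prongs 4; non-invasive ventilation or high-flow oxygen 5; intubation or mechanical ventilation 6; ventilation plus organ support 7; death 8.
- Entry (Protocol 5.1.4 and 5.2.10): patients are hospitalised and not intubated, so in-hospital scores before intubation lie between 3 and 5.
- WHO change endpoint (SAP Outcome Measures): baseline, Days 7, 14 and 28. The Protocol also collects a Day 3 score.
- Arm size: 10 (SAP Sample Size Justification) or 18 (Protocol 15.1).
- Assumptions: the WHO change score is handled as continuous, because the SAP describes methods only for binary, continuous and time-to-discharge endpoints. Where intubation is followed by death, the first event fixes the cut-off; the text does not say.

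**Step 1: size of the understatement.** Understatement = score of the actual state minus worst score before the event.

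| Worst prior score | Ventilated (6) | Ventilated plus organ support (7) | Dead (8) |
|---|---|---|---|
| 5 | 1 | 2 | 3 |
| 4 | 2 | 3 | 4 |

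The range is 1 to 4 points per patient. On a 10-patient arm mean, each such patient contributes 1/10 = 0.1 to 4/10 = 0.4 points.

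**Step 2: early intubation.** On the SAP schedule, a patient intubated before Day 7 has only the baseline score before the event. Worst prior score minus baseline = 0, so the patient enters as no change. Using the Protocol's Day 3 score would help only where that score was taken before intubation and was already worse than baseline.

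**Step 3: missing-only reading (SAP).** Take a patient with baseline 4 who is intubated on Day 5, scored 7 on Day 7 and missing on Day 14. The Day 7 value stays. The Day 14 value must come from before Day 5. If it is 4, it lies 7 − 4 = 3 points below the last score actually measured. The defect therefore remains even when only gaps are filled.

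**Step 4: literal reading (Protocol).** Measured values are replaced as well. A patient discharged early and scored 1 or 2 at Day 28 is entered at the last in-hospital score, which is 3 or more. That is too harsh by at least 3 − 2 = 1 point.

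**Step 5: direction.** A patient who is extubated and recovers to 1, 2 or 3 by Day 28 is entered on the literal reading at a worst prior score of 4 or 5. That is too harsh by 4 − 3 = 1 to 5 − 1 = 4 points. The net direction therefore depends on the mix of patients.

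**Step 6: SpO2/FiO2 (Protocol endpoint), with assumed values.** Before intubation 92/0.60 = 153; on the ventilator 90/1.0 = 90. The difference is 63 points. The shift in an arm mean per patient is 63/10 = 6.3 points with 10 per arm, or 63/18 = 3.5 with 18 per arm.

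**The case against.** The strongest reply is that Protocol 15 defers analysis detail to the SAP, and the SAP places the rule under a missing-data heading. On that wording, values measured after the event are kept. This largely stands: a reader might infer from 15.5 that post-event measurements will certainly be discarded, and the documents taken together do not establish that. What remains is a difference in wording that needs settling, plus the missing-visit and death cases of Steps 1 to 3, which survive the SAP reading.

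A reader might also infer that safety data are carried forward, because Protocol 3.2.2 lists "mean change from baseline lab values, vital signs, and ECG" among the secondary endpoints and 15.5 makes no exemption. The documents do not support stating that as fact. The Safety Summaries part of Protocol 15.3 presents absolute values and changes descriptively, lists out-of-range laboratory results and does not mention imputation. The SAP's safety assessments comprise adverse events only. It is an open point that one sentence would close.

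A third tempting reading is that the rule always flatters the arm with more intubations. Step 5 shows that it does not on the literal reading.

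Setting aside values after rescue is also a recognised choice, since analysing them as measured credits the rescue drug's effect to the randomised arm. That objection stands and is reflected in the fix. Finally, SpO2/FiO2 is not among the SAP's endpoints, so the practical exposure under the SAP is mainly the WHO change score.

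**Conclusion.** The point holds in a limited form. The rule as written, in both documents, gives a milder value than the state it represents whenever a patient who is ventilated or has died has no measured WHO score at a visit. The error is 1 to 4 points per patient, or 0.1 to 0.4 points on a 10-patient arm mean. This assumes that the WHO change score is treated as continuous, that the worst prior score is 4 or 5, and that the first event sets the cut-off. The SpO2/FiO2 shift of 6.3 or 3.5 points per patient is an illustration on assumed values.

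Whether measured values are also replaced depends on which document governs, and the two must be reconciled. The net bias has no fixed sign on the literal reading. The primary endpoint is not touched. The secondary endpoints are supportive in a trial described as hypothesis generating, with no formal hypothesis test planned. The change is still worth making, because the rule works against its own purpose and is easily corrected.

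**What to change.** Use the same wording in Protocol 15.5 and in SAP Missing Data Imputation:

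1. Apply last- and worst-observation carry-forward only to values that are missing. Keep values measured after discharge or intubation. State separately how values after rescue treatment are handled, because that choice defines the estimand.
2. For a value missing after a negative event, use the worst value measured at any time up to that visit, including after the event. Score death as 8 on the WHO scale. This is deliberately severe for a patient who recovers and then misses a visit, in keeping with the purpose of a worst-value rule.
3. State that the descriptive laboratory, vital-sign and ECG summaries use observed values.

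The SAP should also say that the WHO change score is analysed as continuous, if that is the intention. The cost is a few sentences in each document and the matching programming. No new data are needed, because the Protocol already requires the post-event measurements.

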#### 15.6 Multiplicity

This is an early pilot study with a single primary endpoint. All secondary endpoints are considered supportive to the primary. The study is hypothesis generating and not intended to support definitive label claims. Therefore, no measures to control for multiplicity will be implemented in the statistical analyses for this study.

#### 15.7 Study Stopping Rules

If 10% or more of the patients evaluated cumulatively every two weeks demonstrate any adverse event of grade 3 or higher that is attributable to the investigational agent and that is not alleviated or controlled by appropriate care or antibiotic therapy within 14 days, will trigger a full review by the data safety

monitoring committee to determine the appropriate course of action. The DSMB may request suspension of the study to allow time for a full committee review or may permit the study to continue after formal review. The DSMB can, however, request a full review at any time in response to an unexpected toxicity regardless of whether the 10% threshold is met.

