### 1.4 Measures to Minimize Bias: Randomization and Blinding

This study is randomized and double-blinded to reduce or avoid bias. A randomization schedule will be generated by an independent unblinded statistician prior to the start of the study. Furthermore, consecutive participants will be randomized according to the randomization schedule to further avoid bias.

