### 11.2 Dose Modification Guidelines

A patient experiencing a SAE will be evaluated for whether this is attributable to the drug or due to the patient's disease progression course in order to determine whether the patient should remain on study treatment.

Dose modifications are not permitted in this study.

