#### **16.1.2 Relationship To Study Agent**

The relationship to study intervention or study participation must be assessed and documented for all adverse events. Evaluation of relatedness must consider etiologies such as natural history of the underlying disease, concurrent illness, concomitant therapy, study-related procedures, accidents, and other external factors.

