## 18.2 Review of Serious Adverse Event Rates

Once every two weeks, serious adverse event rates will be monitored by the DSMB Coordinator. If any study site has had 2 or more of the same treatment-related SAE reported within one month, or more than 6 of the same treatment-related SAE in 3 months, the DSMB will review summaries of SAEs, and discuss events in detail with the PI. The DSMB chair or designee determines whether further action is required. The Sponsor/Investigator, in collaboration with the DSMB Coordinator ensure that collaborating investigators and IRBs for all participating sites are notified of any resulting action.

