### Suspected Adverse Reaction

A Suspected Adverse Reaction (SAR) is any AE for which there is a reasonable possibility that it was caused by the drug.

Reasonable possibility means there is evidence to suggest a causal relationship between the drug and the AE. Examples of reasonable possibility are:

- A single occurrence of an event that is uncommon and known to be strongly associated with drug exposure.
- One or more occurrences of an event that is not commonly associated with drug exposure but is otherwise uncommon in the population exposed to the drug.
- An aggregate analysis of specific events observed in a clinical trial that indicates that those events occur more frequently in the drug treatment group than in a concurrent or historical control group.

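### Both numerical triggers for DSMB review count only drug-attributed events and ignore arm, so an excess of deaths or intubations judged to be COVID-19 adds nothing to either

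*Protocol*

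**What the plan says.** Two places in the Protocol set a numerical condition that obliges the DSMB to review the study.

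- Section 15.7: the event counted is "any adverse event of grade 3 or higher that is attributable to the investigational agent", provided it stays uncontrolled for 14 days. A full review follows once the share affected reaches the threshold, which is worded "If 10% or more of the patients evaluated cumulatively every two weeks". No arm is named.
- Section 18.2: a site reporting "2 or more of the same treatment-related SAE reported within one month, or more than 6 of the same treatment-related SAE in 3 months" prompts a DSMB review of SAE summaries and a detailed discussion with the PI.

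Attribution is made patient by patient. Section 11.2 has a patient with an SAE "evaluated for whether this is attributable to the drug or due to the patient's disease progression course". Section 16.1.2 adds: "Evaluation of relatedness must consider etiologies such as natural history of the underlying disease". Section 1.4 makes the trial double-blind, and 15.4 rules out an interim analysis.

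Appendix A, under Suspected Adverse Reaction, accepts as evidence of causality "An aggregate analysis of specific events observed in a clinical trial that indicates that those events occur more frequently in the drug treatment group", judged against controls. No section says who makes that comparison, or when.

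**The concern.** Death and intubation are negative intercurrent events for the primary endpoint (15.5), and they are also the natural course of the disease being treated. A single case report cannot show whether the drug made a patient's deterioration more likely. A comparison of randomised arms can give evidence on that, and Appendix A accepts this kind of evidence. The two numerical triggers do not use it. They ask for the causal answer first and then count.

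At stake is whether the pre-specified rules, followed exactly, could let a substantial excess of deaths or intubations on ATI-450 build up without obliging anyone to compare the arms.

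**Working it through.** **Inputs from the documents.** The 15.7 threshold is 10% of patients. The sample size is 20 (10 per arm) in the SAP and 36 (18 per arm) in Protocol 15.1. No operating characteristics are given for either trigger, so there is no figure to reproduce.

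**Assumptions.** The documents give no death or intubation rate and no attribution rate. I take 20% for death or intubation on placebo, vary the rate on ATI-450, and let a fraction q of events be attributed to drug equally in both arms. Every attributed event is treated as uncontrolled at 14 days. Looks fall after each 1:1 pair with outcomes known at once, which simplifies the two-weekly cycle. Results for repeated looks come from simulation with at least 100,000 trials per scenario.

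**Step 1: threshold as a count.** Patients needed = ceil(0.10 × N): 2 of 20, 4 of 36, and 1 whenever N is 10 or fewer.

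**Step 2: nothing attributed.** With q = 0 the count is 0 and neither trigger can fire because of these events, whatever the true excess. This follows from the wording and needs no assumed event rate.

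**Step 3: some events attributed.** Take q = 0.10 and rates of 20% and 50%. The per-patient probabilities of a counted event are 0.02 and 0.05. At full enrolment with 10 per arm:

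- P(0) = 0.98^10 × 0.95^10 = 0.489
- P(1) = 0.489 × (10 × 0.02/0.98 + 10 × 0.05/0.95) = 0.357
- P(2 or more) = 1 − 0.489 − 0.357 = 0.15

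Exchanging 0.02 and 0.05 between the arms leaves this unchanged. Over all looks the probability is 0.33 under harm and 0.33 with the rates reversed. Most of the rise from 0.15 comes from looks at 10 or fewer patients, where one event suffices. With q = 0.30 the rule fires in 77% of trials at 20% versus 50%, and with q = 0.50 in 94%. A higher q makes it fire more often, but it still ignores which arm the events are in.

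**Step 4: dropping attribution alone is not enough.** With both arms at 20%, a pooled all-cause count reaches 10% by full enrolment in 93% of trials (N = 20) or 95% (N = 36).

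**Step 5: attribution-free excess by arm.** Review is prompted when patients with death or intubation on ATI-450 exceed those on placebo by the margin at any look.

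| Per arm | Margin | Placebo vs ATI-450 | Probability of firing |
|---|---|---|---|
| 10 | 3 | 20% vs 50% | 66% |
| 10 | 3 | 20% vs 40% | 46% |
| 10 | 3 | 20% vs 30% | 26% |
| 10 | 3 | 20% vs 20% | 10% |
| 18 | 3 | 20% vs 20% | 22% |
| 18 | 4 | 20% vs 50% | 81% |
| 18 | 4 | 20% vs 20% | 10% |

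Counted only once, at full enrolment with 10 per arm, the exact binomial values for a margin of 3 are 60% (20% vs 50%) and 8% (20% vs 20%).

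**The case against.** The strongest reply is that the DSMB is not confined to these triggers. Section 9.1.3 sends it each grade 3 or higher toxicity within 24 hours, before attribution is settled. Section 16.2.3 notifies it automatically of SAEs whatever their cause. Section 18.3 has it review toxicities overall, and section 18 gives it authority to suspend or terminate. It may also call a full review for unexpected toxicity (15.7). All of this stands. A reader might infer that an excess of deaths need never reach a DSMB review; the documents do not support that. What remains is narrower: none of these routes, as written, calls for a comparison by arm or sets a threshold.

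Second, by-arm tables may already exist. The SAP refers to attached DSMB table shells, and section 18 to a Data and Safety Monitoring Plan; neither is in the text. The documents also do not say whether the DSMB sees allocation, so its blinding cannot be assumed. Both points stand, and the fix allows for them.

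Third, the attribution bar may be low: 16.1.2 counts a possible relation as related, so it is not established that most such events would be called unrelated. That is fair, although Appendix A lists only definite and unrelated, which leaves the bar uncertain. New bacterial or fungal infection is a weaker example of the gap, since it is already an event of special interest reported regardless of severity.

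Fourth, a numerical by-arm trigger may seem excessive in a small hypothesis-generating trial, and its yield is modest. The yield is indeed modest. That is a reason to make it prompt a review only.

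**Conclusion.** The concern holds for the two numerical triggers. Deaths and intubations judged to be COVID-19 count zero towards both at any true excess on ATI-450. Attributed events count without regard to arm, so 15.7 fires equally often under harm and under the mirror-image benefit when attribution is equal across arms. The first statement rests on the wording alone. The percentages rest on assumed event and attribution rates and on looks after each pair.

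A reader might also infer that the placebo arm would reveal such an excess. At 10 per arm that is too strong: a margin of 3 catches 20% versus 50% in about two trials in three, but 20% versus 40% in fewer than half. The supportable statement is that a comparison by arm could help reveal a large excess and will miss small ones. This is an inexpensive improvement to the monitoring plan; it does not show that the trial lacks safety oversight.

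**What to change.** State in 15.7 and 18.2 that at each two-weekly review an unblinded statistician gives the DSMB, in closed session, cumulative counts by arm of all-cause deaths, intubations, all SAEs and new bacterial or fungal infections, regardless of attribution. If the DSMB shells already provide this, say so and cite them. State whether the DSMB sees allocation.

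Add a trigger for full DSMB review, not automatic stopping, when the number of ATI-450 patients with death or intubation exceeds the placebo number by a pre-set margin. Tie the margin to the final sample size: in the illustration, 3 with 10 per arm and 4 with 18 per arm each give about 10% false alarms with both arms at 20%. Keep arm-level data out of the 18.2 discussion with the PI.

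The cost is Protocol and monitoring-plan wording, one small table every two weeks from data already collected, and some false-alarm reviews (about 3% to 15% of trials with 10 per arm, a margin of 3 and equal rates of 10% to 30%). It also modestly extends a role: section 1.4 says only that "A randomization schedule will be generated by an independent unblinded statistician prior to the start of the study", and gives that statistician no reporting task.
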